9.1. Definition of Adverse Event

Adverse Event Definition

- An AE is any untoward medical occurrence associated with the use of a drug in humans, whether or not it is considered drug related.
- An AE can therefore be any unfavorable or unintended sign (including an abnormal laboratory finding), symptom, or disease (new or exacerbated) temporally associated with the use of study drug.

Additional Guidance for Events Meeting the Adverse Event Definition

- Any safety assessments (eg, vital signs measurements), including those that worsen from baseline, considered clinically significant in the medical and scientific judgment of the investigator (ie, not related to progression of underlying disease) are to be reported as an AE.
- Abnormal laboratory test results are to be reported as an AE if they are considered clinically meaningful, induce clinical signs or symptoms, require concomitant therapy, or require changes in study drug. Whenever possible, a diagnosis (eg, anemia, thrombocytopenia) should be recorded in the eCRF rather than the abnormal laboratory test result (eg, low hemoglobin, platelet count decreased).
- Exacerbation of a chronic or intermittent pre-existing condition/disease, including either an increase in the frequency and/or intensity of the condition, is to be reported as an AE.
- New conditions detected or diagnosed after the start of study drug administration are to be reported as an AE.
- Signs, symptoms, or the clinical sequelae of a suspected drug-drug interaction are to be reported as an AE.
- Signs and/or symptoms from dose administration errors of a study drug (eg, overdose) or a concomitant medication are to be reported as an AE.
- "Lack of efficacy," "disease progression," or "failure of expected pharmacological action" will not be reported as an AE or SAE. Such instances will be captured in the efficacy assessments.
- A condition that leads to a medical or surgical procedure (eg, endoscopy, appendectomy) will be reported as an AE if it occurs after obtaining informed consent. If the condition is present before entering the study, then it should be captured as medical history.
- Pre-existing diseases or conditions with expected fluctuations in signs or symptoms should be reported as an AE only if the investigator judges the fluctuation to have worsened more than expected during study participation.

9.2. Definition of Serious Adverse Event

If an event is not an AE per the definition above, then it cannot be an SAE even if serious conditions are met (eg, hospitalization for signs/symptoms of the disease under study, death due to progression of disease).

A serious adverse event is defined as any untoward medical occurrence that, at any dose:

a. Results in death

b. Is life-threatening

The term "life-threatening" in the definition of "serious" refers to an adverse drug experience that places the participant, in the opinion of the initial reporter, at immediate risk of death from the adverse experience as it occurs. This does not include an adverse drug experience that, had it occurred in a more severe form, might have caused death.

c. Requires inpatient hospitalization or prolongation of existing hospitalization

In general, hospitalization signifies that the participant has been detained (involving at least an overnight stay) at the hospital or emergency department for observation and/or treatment that would not have been appropriate in the physician's office or outpatient setting. Complications that occur during hospitalization are AEs. If a complication prolongs hospitalization or fulfills any other serious criteria, the event is serious. When in doubt as to whether hospitalization occurred or was necessary, the AE should be considered serious.

Hospitalization for elective treatment or planned surgery (eg, stent replacement, or hip surgery) is not considered an SAE.

Hospitalization for medical interventions in which no unfavorable medical occurrence occurred (ie, elective procedures or routine medical visits) is not considered an SAE.

d. Results in persistent or significant disability/incapacity

The term "disability" means a substantial disruption of a person's ability to conduct normal life functions. This definition is not intended to include experiences of relatively minor medical significance, such as uncomplicated headache, nausea, vomiting, diarrhea, influenza, and accidental trauma (eg, sprained ankle) that may interfere with or prevent everyday life functions but do not constitute a substantial disruption.

e. Is a congenital anomaly/birth defect

f. Is an important medical event

An important medical event is an event that may not result in death, be immediately life-threatening, or require hospitalization but may be considered serious when, based on appropriate medical judgment, the event may jeopardize the participant and may require medical or surgical intervention to prevent one of the outcomes listed in the above definition. Examples of such events include new invasive or malignant cancers; intensive treatment in an emergency department or at home for allergic bronchospasm, blood dyscrasias, or convulsions that do not result in hospitalization; development of drug dependency or drug abuse; or suspected transmission of an infectious agent via a medicinal product.

9.3. Recording and Follow-Up of Adverse Events and/or Serious Adverse Events

Adverse Event and Serious Adverse Event Recording

- An AE/SAE that begins or worsens after informed consent is signed should be recorded on the Adverse Events Form in the eCRF. All AEs/SAEs should be reported for enrolled participants, but only SAEs need to be reported for screen failure participants. For enrolled participants, conditions that were present at the time informed consent was given should be recorded on the Medical History Form in the eCRF. For detailed information, refer to the eCRF guidelines.
- When an AE/SAE occurs, it is the responsibility of the investigator to review all documentation (eg, hospital progress notes, laboratory reports, and diagnostic reports) related to the event.
- The investigator (or designee) will then record all relevant AE/SAE information in the eCRF.
- It is **not** acceptable for the investigator to send photocopies of the participant's medical records in lieu of completing the Adverse Events Form in the eCRF.
- There may be rare instances when copies of medical records for certain cases are requested. In this case, all participant identifiers, with the exception of the participant number, will be redacted by the site staff on the copies of the medical records before submission. These records can be submitted to Incyte Pharmacovigilance by email/fax per the contact information listed as per SAE completing guidelines.
- The investigator will attempt to establish a diagnosis of the event based on signs, symptoms, and/or other clinical information. Whenever possible, the diagnosis (not the individual signs/symptoms) will be documented as the AE/SAE. When a clear diagnosis cannot be identified, each sign or symptom should be reported as a separate AE/SAE.

To the extent possible, each AE/SAE should be evaluated to determine the following:

- The severity grade (CTCAE v5.0 Grade 1 to 5). See below for further instructions on the assessment of intensity.
- Whether there is at least a reasonable possibility that the AE is related to the study drug: suspected (yes) or not suspected (no). See below for further instructions on the assessment of causality.
- The start and end dates, unless unresolved at the final safety follow-up visit.
- The action taken with regard to study drug as a result of the AE/SAE(s).
- The event outcome (eg, not recovered/not resolved, recovered/resolved, recovering/resolving, recovered/resolved with sequelae, fatal, unknown).
- The seriousness, as per the SAE definition provided in Section 9.2.
- The action taken with regard to the event. Note: If an AE is treated with a concomitant medication or nondrug therapy, this action should be recorded on the Adverse Events Form and the treatment should be specified on the appropriate eCRF (eg, Prior/Concomitant Medications, Procedures, and Non-drug Therapy).

Assessment of Intensity

The severity of AEs will be assessed using CTCAE v5.0 Grades 1 through 5. If an event is not classified by CTCAE, the severity of the AE will be graded according to the scale below to estimate the grade of severity.

The investigator will make an assessment of intensity for each AE and SAE reported during the study and assign it to 1 of the following categories:

- **Grade 1:** Mild; asymptomatic or mild symptoms; clinical or diagnostic observations only; treatment not indicated.
- **Grade 2:** Moderate; minimal, local, or noninvasive treatment indicated; limiting age-appropriate activities of daily living.
- **Grade 3:** Severe or medically significant but not immediately life-threatening; hospitalization or prolongation of hospitalization indicated; disabling; limiting self-care activities of daily living.
- Grade 4: Life-threatening consequences; urgent treatment indicated.
- Grade 5: Fatal.

Assessment of Causality

- The investigator is obligated to assess the relationship between study drug and each occurrence of each AE/SAE.
- A "reasonable possibility" of a relationship conveys that there are medical facts, evidence, and/or arguments to suggest a causal relationship, rather than that a relationship cannot be ruled out.
- The investigator will use clinical judgment to determine the possibility of a relationship.
- The investigator will also consult the RSI in the IB in making their assessment.
- Alternative causes, such as underlying or concurrent disease(s), concomitant therapy, and other risk factors, as well as the temporal relationship of the event to study drug administration, will be considered and investigated.
- For each AE/SAE, the investigator **must** document in the medical notes that they have reviewed the AE/SAE and have provided an assessment of causality.
- With regard to assessing causality of SAEs:
 - There may be situations in which an SAE has occurred, and the investigator has minimal information to include in the initial report. However, the causality assessment is one of the criteria used when determining regulatory reporting requirements. Therefore, it is very important that the investigator always make an assessment of causality based on the available information for every event before the initial transmission of the SAE.
 - The investigator may change their opinion of causality in light of follow-up information and submit the updated causality assessment.

Follow-Up of Adverse Events and Serious Adverse Events

• The investigator is obligated to perform or arrange for the conduct of supplemental measurements and/or evaluations as medically indicated or as requested by the sponsor to elucidate the nature and/or causality of the AE or SAE as fully as possible. This may include additional laboratory tests or investigations, histopathological examinations, or consultation with other health care professionals.

- Once an AE is detected, it should be followed in the Adverse Events Form in the eCRF until it has resolved or until it is judged to be permanent; assessment should be made at each visit (or more frequently if necessary) of any changes in severity, the suspected relationship to the study drug, the interventions required to treat the event, and the outcome.
- When the severity of an AE changes over time for a reporting period (eg, between visits), each change in severity will be reported as a separate AE.
- If a participant dies during participation in the study or during a recognized follow-up period, the investigator will provide the sponsor with a copy of any postmortem findings, including histopathology.
- Updated SAE information will be recorded in the originally completed eCRF and reported to Incyte Pharmacovigilance (either via email/fax if paper SAE form is used or in the SAE EDC CRF) until resolution, stabilization, the event is otherwise explained, or the participant is lost to follow-up.
- Any updated SAE data (including SAEs being downgraded to nonserious) will be submitted to the sponsor (or designee) immediately, without undue delay but not later than within 24 hours of receipt of the information.

9.4. Reporting of Serious Adverse Events

Regardless of suspected causality (eg, relationship to study drug or study procedure[s]), all SAEs occurring after the participant has signed the ICF through at least 30 days after the last application of study drug must be reported to the sponsor (or designee) immediately, without undue delay but not later than within **24 hours** of obtaining knowledge of its occurrence unless otherwise specified by the Protocol. The investigator will submit any updated SAE data to the sponsor (or designee) immediately, without undue delay but not later than within 24 hours of it being available.

Investigators are not obligated to actively seek SAE information after the safety follow-up visit or 30 days after the last dose of study drug. If the investigator learns of any SAE, including death, at any time during this period, and they consider the event to be reasonably related to the study drug or study participation, then the investigator must notify the sponsor (or designee) immediately, without undue delay but not later than within 24 hours of becoming aware of the event.

After the initial AE/SAE report, the investigator is required to proactively follow each participant at subsequent visits/contacts. All SAEs will be followed until resolution, stabilization, the event is otherwise explained, or the participant is lost to follow-up (as defined in Section 7.3).

Prompt notification by the investigator to the sponsor regarding an SAE is essential so that legal obligations and ethical responsibilities for the safety of participants and the safety of a study drug under clinical investigation are met.

If the SAE is not documented in the RSI of the IB for the study drug (new occurrence) and is thought to be related to the study drug, the sponsor or its designee may urgently require further information from the investigator for expedited reporting to health authorities. The sponsor or its designee may need to issue an Investigator Notification to inform all investigators involved in any study with the same drug that this SAE has been reported. Suspected unexpected serious adverse reactions will be collected and reported to the competent authorities and relevant ethics committees in accordance with Clinical Trials Regulation (EU) No. 536/2014 or per national regulatory requirements in participating countries.

The sponsor has a legal responsibility to notify both the local regulatory authority and other regulatory agencies about the safety of a study drug under clinical investigation. The sponsor will comply with country-specific regulatory requirements relating to safety reporting to the regulatory authority, IRB/IEC, and investigators.

Investigator safety reports must be prepared for suspected unexpected serious adverse reactions according to local regulatory requirements and sponsor policy and forwarded to investigators as necessary.

An investigator who receives an investigator safety report describing an SAE or other specific safety information (eg, summary or listing of SAEs) from the sponsor will review and then file it along with the IB and will notify the IRB/IEC, if appropriate, according to local requirements.

Serious Adverse Event Reporting

- Information about all SAEs is collected and recorded on the Adverse Events Form in the eCRF.
- The investigator must report immediately, without undue delay but not later than within 24 hours of learning of its occurrence, any SAE via the EDC system (primary method) or by completing the Serious Adverse Event Report Form in English (only if the EDC system is not available). The contact information for Incyte Pharmacovigilance by email/fax is listed in the Study Reference Manual or the Incyte Reference Guide for Completing the Serious Adverse Event Report Form.
- In circumstances where the EDC system is not accessible for reporting SAE information (initial and/or follow-up SAE information) to the sponsor within 24 hours, refer to the Incyte Reference Guide for Completing the Serious Adverse Event Report Form. Once the EDC system is functional, the SAE report should be retrospectively added to the EDC system and follow-up should be completed through the EDC. The original copy of the Serious Adverse Event Report Form and the email or facsimile confirmation sheet must be kept at the study site (refer to the Incyte Reference Guide for Completing the Serious Adverse Event Report Form or Study Reference Manual for details and for the email address or fax number).
- Follow-up information is also recorded in the eCRF and transmitted to Incyte Pharmacovigilance via the EDC system. The follow-up report should include information that was not provided previously, such as the outcome of the event, treatment provided, action taken with study drug because of the SAE (eg, dose reduced, interrupted, or discontinued), or participant disposition (eg, continued or withdrew from study participation). Each recurrence, complication, or progression of the original event should be reported as follow-up to that event, regardless of when it occurs.

9.5. Potential Drug-Induced Liver Injury

Not applicable.

9.6. Events of Clinical Interest

Not applicable.

9.6.1. Adverse Events of Special Interest

Not applicable.

9.7. Emergency Unblinding of Treatment Assignment

In case of a medical emergency, for a participant's safety management, the procedure for emergency unblinding is provided to the investigator in the IRT Manual. The IRT system has an option to select for "Emergency Code Break" action for a given participant. After entering the study drug tube number and verification of the unmasking information, the investigator/subinvestigator will proceed to either final confirmation or cancellation of the code break procedure.

If a participant's treatment assignment is unblinded, the sponsor or its designee should be notified immediately by telephone/email/IRT for awareness.

If an investigator, the site personnel performing assessments, or a participant is unblinded, then the participant must discontinue study drug unless there are ethical reasons to have the participant remain on the study drug. In these cases, the investigator must obtain specific approval from the sponsor's (or its designee's) medical monitor for the participant to continue in the study.

9.8. Pregnancy

Pregnancy, in and of itself, is not regarded as an AE unless there is suspicion that the study drug may have interfered with the effectiveness of a contraceptive medication or method. When a pregnancy has been confirmed in a participant during maternal or paternal exposure to study drug, the following procedures should be followed in order to ensure safety:

- The study drug must be discontinued immediately.
- The investigator must complete and submit the Incyte Clinical Trial Pregnancy Form to the sponsor or its designee within **24 hours** of learning of the pregnancy.

Data on fetal outcome are collected for regulatory reporting and drug safety evaluations. Follow-up should be conducted for each pregnancy to determine outcome, including spontaneous or voluntary termination, details of the birth, and the presence or absence of any birth defects, congenital abnormalities, or maternal and/or newborn complications, by following until the first well-baby visit. Pregnancy should be recorded on a Clinical Trial Pregnancy Form and reported by the investigator to the sponsor or its designee. Pregnancy follow-up information should be recorded on the same form and should include an assessment of the possible causal relationship to the sponsor's study drug to any pregnancy outcome, as well as follow-up to the first well-baby visit or the duration specified in local regulations, whichever is later. Refer to the Incyte Reference Guide for Completing the Clinical Trial Pregnancy Form.

Any SAE occurring during the pregnancy of a study participant must be recorded and reported as described in Section 9.4.

Abnormal pregnancy outcomes (eg, spontaneous abortion, fetal death, stillbirth, congenital anomalies, or ectopic pregnancy) are considered SAEs (if occurring in the study participant) and must be reported as described in Section 9.4. If an abnormal pregnancy outcome is reported in a study participant's partner, the event should be reported to the sponsor on the Clinical Trial Pregnancy Form.

9.9. Warnings and Precautions

Special warnings or precautions for the study drug, derived from safety information collected by the sponsor or its designee, are presented in the IB. Additional safety information collected between IB updates will be communicated in the form of Investigator Notifications. Any important new safety information should be discussed with the participant during the study as necessary. If new significant risks are identified, they will be added to the ICF.

There are no study-specific warnings or precautions in this study.

9.10. Product Complaints

The sponsor collects product complaints on study drugs and drug delivery systems used in clinical studies in order to ensure the safety of study participants, monitor quality, and facilitate process and product improvements.

All product complaints associated with material packaged, labeled, and released by the sponsor or its designee will be reported to the sponsor. All product complaints associated with other study material will be reported directly to the respective manufacturer.

The investigator or their designee is responsible for reporting a complete description of the product complaint via email or other written communication to the sponsor contact or respective manufacturer as noted in the packaging information. Any AE associated with a product complaint should be recorded as described in Section 9.3.

If the investigator is asked to return the product for investigation, they will return a copy of the product complaint communication with the product.

9.11. Treatment of Overdose

There has been no clinical experience with overdose resulting from excessive use of ruxolitinib cream. Treatment of overdose should consist of general supportive measures.

10. STATISTICS

This section outlines the statistical analysis strategy and procedures for this study. If, after the study has begun, but before the final database lock, changes are made to primary and/or secondary analysis hypotheses or the statistical methods related to those hypotheses, the Protocol may be amended, consistent with ICH E9 (1998) and ICH E9 (R1) (2021). The detailed statistical analyses will be documented in the SAP.

10.1. Sample Size Determination

Approximately 180 participants will be randomized 1:1 to ruxolitinib 1.5% cream BID or vehicle cream BID.

The sample size is calculated to provide sufficient power (> 80%) to detect a difference between ruxolitinib 1.5% cream BID and vehicle cream BID for the primary and key secondary endpoints. The powers for different endpoints are provided in Table 9. The chi-square test with a 2-sided α of 0.05 is used to calculate the powers.

In addition to providing sufficient power for efficacy variables, the sample size is determined to provide an adequate database for safety evaluations.

Table 9: Powering for Primary and Key Secondary Endpoints

Variables	Response Rates With Ruxolitinib 1.5% Cream BID	Response Rates With Vehicle Cream BID	Power
IGA-CHE-TS at Week 16	26% ^{ab}	10% ^{abc}	80%
ITCH4 at Week 16	40% ^{bc}	18% ^{bc}	90%
ITCH4 at Week 4	35% ^{bc}	12% ^{bc}	95%
ITCH4 on Day 7	30% ^{bc}	10% ^{bc}	92%

^a Based on the results from a Phase 2b study of topical delgocitinib in CHE (Worm 2022).

^b Based on the results from a Phase 3 study of topical delgocitinib in CHE (Bissonnette 2023).

^c Based on the results from the 2 Phase 3 registrational AD studies, INCB 18424-303 and INCB 18424-304.

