10.3. Level of Significance

The gatekeeping testing strategy for the primary and key secondary analyses will be implemented to control the overall Type I error rate, 2-sided $\alpha = 0.05$. These endpoints will be tested in a fixed sequence at 2-sided $\alpha = 0.05$ level in the following order:

- IGA-CHE-TS at Week 16
- ITCH4 response at Week 16
- ITCH4 response at Week 4
- ITCH4 response at Week 1 (Day 7)

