10.4.2. Key Secondary Objective

If the primary objective is achieved, the statistical hypotheses for the key secondary endpoint will be tested in the order specified in Section 10.3. Key secondary efficacy analysis at Week 16, Week 4, and Week 1 (Day 7) will be conducted in the ITT population. The statistical comparisons for binary outcomes (ITCH4) will be analyzed using a similar method as specified in the primary analysis. The stratum-adjusted ITCH4 rate difference (1.5% BID vs vehicle) and 95% CI will be computed in a similar way as in the primary analysis. A summary of analyses for the key secondary endpoints is provided in Table 12.

Table 12: Summary of Analyses for Key Secondary Endpoints

Parameter	Definition
Treatment	Ruxolitinib 1.5% cream compared with vehicle cream
Population	ITT population
Variables	ITCH4 response at Week 16: Defined as a ≥ 4-point improvement in CHE-related Itch NRS score from baseline ITCH4 response at Week 4 ITCH4 response at Week 1 (Day 7)
Population-level summary	Stratum-adjusted IGA-CHE-TS rate difference with 95% CI

Note: Participants with missing observed data at the timepoint of interest, participants who discontinue study treatment at any time before the timepoint of interest, and participants who discontinue from the study for any reason will be defined as nonresponders. No rescue therapy or treatment switch is allowed in this study.

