## 3.2. Control of Type I Error

The gatekeeping testing strategy for the primary and key secondary analyses will be implemented to control the overall Type I error rate, 2-sided  $\alpha = 0.05$ . These endpoints will be tested in a fixed sequence at 2-sided  $\alpha = 0.05$  level in the following order:

- IGA-CHE-TS at Week 16
- ITCH4 response at Week 16
- ITCH4 response at Week 4
- ITCH4 response at Week 1 (Day 7)

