## 3.3. Sample Size Considerations

Approximately 180 participants will be randomized 1:1 to ruxolitinib 1.5% cream BID or vehicle cream BID.

The sample size is calculated to provide sufficient power (> 80%) to detect a difference between ruxolitinib 1.5% cream BID and vehicle cream BID for the primary and key secondary endpoints. The powers for different endpoints are provided in Table 2. The chi-square test with a 2-sided  $\alpha$  of 0.05 is used to calculate the powers.

In addition to providing sufficient power for efficacy variables, the sample size is determined to provide an adequate database for safety evaluations.

**Table 2:** Powering for Primary and Key Secondary Endpoints

Variables	Response Rates With Ruxolitinib 1.5% Cream BID	Response Rates With Vehicle Cream BID	Power
IGA-CHE-TS at Week 16	26% a,b	10%a,b,c	80%
ITCH4 at Week 16	40%b,c	18%b,c	90%
ITCH4 at Week 4	35% b,c	12%b,c	95%
ITCH4 on Day 7	30%b,c	10%b,c	92%

<sup>a Based on the results from a Phase 2b study of topical delgocitinib in CHE (Worm et al 2022).

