## 7.4.2. Key Secondary Efficacy Analysis

Key secondary efficacy analyses will be conducted in the ITT population in the DBVC period. If the primary objective is achieved, the statistical comparisons for key secondary endpoints will be tested with the procedures specified in Section 3.2. The same nonresponder imputation method as specified in the primary analysis will be used to handle missing Week 4 and Week 16 itch data.

For the key secondary endpoints of ITCH4 at Week 1 (Day 7), all participants who are missing Day 7 daily Itch NRS scores will be imputed using multiple imputation by fully conditional specification method. The variables to be included in the imputation regression model are treatment group, stratification factor, baseline itch score, and postbaseline daily itch score on Day 1 to Day 7. The corresponding binary response on Day 7 will be derived for each of the imputed datasets per the definition in Section 7.4.1.1.

The following sample SAS code will be used for the MI:

```
proc mi data=mi_wide seed=18424226 nimpute=30 out=impute_itch;
class trt01p strat1 strat2;
var trt01p strat1 strat2 base avald1 avald2 avald3 avald4 avald5
avald6 avald7;
fcs regpmm nbiter=30;
run;
```

All key secondary efficacy analyses will use stratified CMH test similar to the primary efficacy analysis. The summary of key secondary endpoints analysis is also provided in Table 5.

**Table 5:** Summary of Analyses for Key Secondary Endpoints

Parameter	Definition	
Treatment	Ruxolitinib 1.5% cream compared with vehicle cream	
Population	ITT population	
Variables	ITCH4 response at Week 16 ITCH4 response at Week 4 ITCH4 response at Week 1 (Day 7)	
Population-level summary	Stratum-adjusted IGA-CHE-TS rate difference with 95% CI	

Note 1: Participants with missing observed data at the timepoint of interest (Week 4, Week 16), participants who discontinue study treatment at any time before the timepoint of interest (Week 4, Week 16), and participants who discontinue from the study for any reason will be defined as nonresponders. Participants with missing observed data at Day 7 will be imputed using multiple imputation by fully conditional specification method. No rescue therapy or treatment switch is allowed in this study. Note 2: ITCH4 is defined as  $a \ge 4$ -point improvement in CHE-related Itch NRS score from baseline.

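### The stated > 80% power for the key secondary endpoints is stand-alone power; under the planned fixed sequence it is about 65–79%, depending on the endpoint and the dependence between endpoints

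*Protocol*

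**What the plan says.** Protocol 10.1: "Approximately 180 participants will be randomized 1:1 to ruxolitinib 1.5% cream BID or vehicle cream BID". That number, the section says, will "provide sufficient power (> 80%) to detect a difference between ruxolitinib 1.5% cream BID and vehicle cream BID for the primary and key secondary endpoints", and the method is given in one sentence: "The chi-square test with a 2-sided α of 0.05 is used to calculate the powers". Table 9 then lists one power per endpoint: 80% for IGA-CHE-TS at Week 16, and 90%, 95% and 92% for ITCH4 at Week 16, Week 4 and Day 7. SAP 3.3 repeats the statement ("The sample size is calculated to provide sufficient power (> 80%) to detect a difference between" the two arms) and the same four figures in its Table 2.

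The testing procedure is set out elsewhere. Protocol 10.3: "These endpoints will be tested in a fixed sequence at 2-sided" α = 0.05, in the order primary, ITCH4 Week 16, ITCH4 Week 4, ITCH4 Day 7. Protocol 10.4.2 adds: "If the primary objective is achieved, the statistical hypotheses for the key secondary endpoint will be tested in the order specified in Section 10.3". SAP 3.2 gives the same order and purpose ("The gatekeeping testing strategy for the primary and key secondary analyses will be implemented to control the overall Type I error rate"), and SAP 7.4.2 the same condition: "If the primary objective is achieved, the statistical comparisons for key secondary endpoints will be tested with the procedures specified in Section 3.2".

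Neither sample-size section calls its figures stand-alone, gives power under the sequence, or states a correlation between endpoints.

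**The concern.** Each row of the power table treats its endpoint as if it were tested alone at the full alpha. The plan does not test the ITCH4 endpoints that way. Each has to wait for the primary and for every ITCH4 test ahead of it, so the chance of declaring it is the chance that the whole chain up to that point succeeds.

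These three endpoints are the only secondary claims under type I error control. Someone who reads 92% for Day 7 as the chance that the trial will declare a Day 7 effect, if the planning rates are true, is reading the wrong quantity. Part of the gap, the primary's own miss rate of about 20%, can be seen by putting the table next to the testing order. The further loss along the sequence cannot be read off either document.

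**Working it through.** **Inputs.** 90 per arm (about 180, randomized 1:1), two-sided α = 0.05, chi-square test, and the response rates in Protocol Table 9 / SAP Table 2. The order is that of Protocol 10.3 / SAP 3.2.

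**Step 1: reproduce the table.** With d = p₁ − p₂ and p̄ the mean of the two rates:

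power = Φ{ [d − 1.96·√(2p̄(1−p̄)/n)] / √([p₁(1−p₁) + p₂(1−p₂)]/n) }

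For the primary (26% vs 10%, p̄ = 0.18): (0.16 − 1.96 × 0.05727)/0.05602 = 0.852, and Φ(0.852) = 80.3%. The exact column enumerates the uncorrected chi-square over all 91 × 91 outcomes.

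| Endpoint | Rates | Plan | Formula | Exact |
|---|---|---|---|---|
| IGA-CHE-TS Week 16 | 26% vs 10% | 80% | 80.3% | 81.2% |
| ITCH4 Week 16 | 40% vs 18% | 90% | 90.9% | 91.1% |
| ITCH4 Week 4 | 35% vs 12% | 95% | 95.9% | 96.3% |
| ITCH4 Day 7 | 30% vs 10% | 92% | 92.5% | 93.2% |

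The plan's figures reproduce as stand-alone powers.

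**Step 2: bounds that need no assumption about dependence.** An endpoint in the sequence is declared only if all tests up to it reject.

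- Ceiling = smallest stand-alone power up to that step. For all three ITCH4 endpoints this is the primary's: 80.3% (formula) or 81.2% (exact).
- Floor = sum of the powers minus (number of tests − 1). By formula:
  - Week 16: 0.8030 + 0.9086 − 1 = 71.2%
  - Week 4: 0.8030 + 0.9086 + 0.9594 − 2 = 67.1%
  - Day 7: 0.8030 + 0.9086 + 0.9594 + 0.9250 − 3 = 59.6%

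  With exact powers the floor is about 72/69/62%.

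**Step 3: independence.** The product of the powers gives 73.0/70.0/64.8% by formula (for Week 16, 0.8030 × 0.9086 = 0.730) and 74.0/71.2/66.3% with exact powers.

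**Step 4: the strongest dependence that the tabled rates allow.** Two binary endpoints with different response rates cannot be perfectly correlated. Their correlation is largest when every responder on the rarer endpoint also responds on the commoner one: φ = √[p_a(1−p_b)/(p_b(1−p_a))] with p_a < p_b.

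- Ruxolitinib, 26% and 40%: √(0.26 × 0.60/(0.40 × 0.74)) = 0.726.
- Vehicle, 10% and 18%: √(0.10 × 0.82/(0.18 × 0.90)) = 0.711.
- Correlation of the two rate differences: (0.156 + 0.082)/√(0.2824 × 0.3876) = 0.238/0.331 = 0.72.

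At 0.72, the bivariate normal probability that the primary and ITCH4 Week 16 both reject is 77.7% with formula powers and 78.6% with exact powers. Participant-level simulation with fully nested responses on all four endpoints (90 per arm, uncorrected chi-square) gives 78.6/78.5/78.5% for Week 16/Week 4/Day 7.

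**Summary.**

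| In-sequence power | Week 16 | Week 4 | Day 7 |
|---|---|---|---|
| Tabled (stand-alone) | 90% | 95% | 92% |
| Ceiling from the primary | 80–81% | 80–81% | 80–81% |
| Fully nested responses | 79% | 79% | 79% |
| Independence | 73–74% | 70–71% | 65–66% |
| Worst-case floor (formula) | 71% | 67% | 60% |

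**The case against.** The best defence is that little is hidden. Protocol 10.1 names the test and alpha behind each figure, one test per row at full alpha is marginal power by construction, and the testing order follows two sections later. No passage claims joint or in-sequence power, and marginal powers are common in sample-size sections. All of this stands. It makes the defect a missing label and an unqualified sentence, not a false table entry.

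It is also true that the cap does not by itself contradict > 80%, since 80.3% and 81.2% both lie just above it. The conclusion needs Step 4, where the documents' own response rates keep in-sequence power below 80%.

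A third objection is that the 71/67/60% floor requires the failures of the successive tests never to overlap. For a severity score and three itch measures in the same participants that is implausible. The floor should be given only as a worst case, not as expected power.

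Three stronger readings may tempt a reader, and the documents support none of them.

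- That the power table is miscalculated: it reproduces.
- That type I error control is at fault: the fixed sequence at full alpha is sound and described consistently in both documents.
- That the trial is too small: neither document sets a target for in-sequence power. If the primary succeeds, the chance of declaring each ITCH4 endpoint is still at least 89/84/74% (floor divided by the primary's power, by formula), given the planning rates.

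**Conclusion.** The point holds as a misstatement of what the sample size delivers. If the tabled rates are true, the planned procedure gives each key secondary endpoint about 73–79% (Week 16), 70–79% (Week 4) and 65–79% (Day 7), from independence to full within-participant dependence. It does not give more than 80%. Against the tabled 90/95/92%, the shortfall is at least about 11, 16 and 13 points (each figure minus 79%).

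The ceiling and floor need no assumption about dependence. The 79% rests on the tabled rates and on complete nesting of responses, the independence figures on no correlation at all. The documents do not say where between these the trial lies. All figures use the plan's unstratified chi-square at exactly 90 per arm, with the tabled rates taken as already allowing for dropout and missing data. The planned tests are stratified CMH tests.

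This should be corrected, but nothing in the design depends on it.

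**What to change.** In Protocol 10.1/Table 9 and in SAP 3.3/Table 2:

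1. Head the power column: *Stand-alone power (not accounting for the fixed sequence)*.
2. In the sample-size sentence, limit > 80% for the key secondary endpoints to stand-alone power.
3. Add a footnote: *Under the fixed sequence, the power for each key secondary endpoint cannot exceed that of the primary (about 80%). With the tabled rates it is about 73–79% / 70–79% / 65–79% for ITCH4 at Week 16 / Week 4 / Day 7, from independence to full within-participant dependence (assumed, since no correlation is available). The worst-case bound is 71% / 67% / 60%.*

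The cost is a heading, a qualifier and a footnote in each document, and a less favourable stated figure. Tests, order, alpha and sample size are unchanged.
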